2. INTRODUCTION

2.1 Background

“Long-COVID” (also known as post-COVID-19 syndrome, post-acute sequelae of COVID-19, or chronic COVID syndrome, used here as ‘Long-COVID’ for brevity), is a complex array of postconvalescence symptoms following SARS-CoV-2 infection. The syndrome, common in COVID-19 survivors, can affect every organ system through as-yet uncharacterised but presumed immunological mechanisms. Prevalence depends on the definition used and time-period of follow-up, as well as the population being studied. The syndrome has been associated with significant and persistent disability in some survivors but has been hampered, until recently, by lack of a clinical definition, diagnostic criteria, and objective measures of disease or disability [1]. A Delphi-informed initial World Health Organisation (WHO) clinical definition was released in early October 2021 but has attracted much criticism from both clinicians and survivors for a host of reasons, ranging from a lack of precision to a lack of inclusion [2].

Further complicating the syndrome is the context in which the SARS-CoV-2 epidemic occurred, which was associated with severe lockdowns in many countries (including South Africa) with social isolation, widespread fear and disinformation, widespread economic hardship, and loss of family and acquaintances, all of which contribute to symptoms (psychiatric and sleep disturbances, pain, and other syndromes) reported to be associated with Long-COVID. Finally, many Long-COVID symptoms overlap with those seen in patients hospitalised for any severe illness, especially those admitted to intensive care and ventilated. However, the proliferation of literature reporting associations of Long-COVID symptoms with more severe COVID-19 disease, and objective immunological, radiological, and organ-specific dysfunction in those reporting symptoms, suggests that the entity is real. The pathogenesis of Long-COVID is poorly understood, but this association with more severe disease - where immune dysregulation plays a major role in those with hospitalization, respiratory failure, and death - suggests an immune-mediated inflammatory dysfunction that may impact all organs [3-14].

The sheer rapidity of four major infection waves in South Africa, the initial focus on containing the hospital burden of those with severe illness, and subsequent emphasis on the roll-out of a mass vaccination program, has left little space for studying SARS-COV-2 sequelae in survivors. This group, loosely and inaccurately termed “recovered” in South African reporting, were largely unvaccinated or partly vaccinated at the time of infection, leaving them at risk of developing Long-COVID.

2.2 Long-COVID

[figure not shown]

Figure 1: Long-term effects of coronavirus disease 2019 (COVID-19). The meta-analysis of the studies included an estimate for one symptom or more reported that 80% of the patients with COVID-19 have long-term symptoms.

CRP = C-reactive protein, CT = computed tomography, IL-6 = Interleukin-6, NT-proBNP = (NT)-pro hormone BNP, OCD = Obsessive Compulsive Disorder, PTSD = Post-traumatic stress disorder.

This figure was created using Biorender.com (Reproduced under a Common Creation Licence, from Lopez-Leon, S., Wegman-Ostrosky, T., Perelman, C. et al [4])

Long-COVID reported symptoms are extraordinarily broad. Over 50 symptoms were reported in a recent review, with over 80% of COVID-19 survivors having at least one symptom, sign, or abnormal

laboratory parameter after infection [4]. Fatigue (58%), headache (44%), attention disorder (27%), hair loss (25%), and dyspnoea (24%) were the most reported symptoms in this review, with abnormal chest x-ray or computed tomography (CT) scan findings detected in 34% of patients. Other symptoms and signs were related to lung disease (cough, chest discomfort, reduced pulmonary diffusing capacity, sleep apnoea, and pulmonary fibrosis), cardiovascular disorders (arrhythmias, myocarditis), neuropsychiatric diseases (dementia, depression, anxiety, obsessive-compulsive disorders), and others were non-specific such as tinnitus and night sweats.

The diagnosis of Long-COVID is one of exclusion, and symptoms may fluctuate although tend to resolve with time. It is unclear whether disability and organ damage may be permanent in some patients. No specific treatment exists, and interventions are typically symptom-directed. SARS-CoV-2 vaccination appears to benefit many symptomatic survivors [15].

At the time of writing, no African data characterising the clinical features of Long-COVID have been published.

2.3 Study Rationale

Characterizing Long-COVID and related disability in local populations is an important first step to understanding the burden of morbidity and potential requirements of the health system in addressing symptoms and disability.

Almost all studies on Long-COVID have been undertaken in higher income countries, and largely in hospitalised patients, with almost no data emerging yet from Africa. This study aims to characterise Long-COVID in South African patients by leveraging an existing patient base (including asymptomatic outpatients, symptomatic outpatients, and hospitalised patients with severe COVID-19) and local research expertise.

The study is anticipated to add significantly to understanding Long-COVID, and to contribute African data to current efforts to develop syndrome diagnostic criteria (including the WHO case definition) and an understanding of the therapeutic needs of symptomatic survivors, thus informing South African health care.

2.3.1 Rationale for specific sub-study focus areas

- **Psychiatric, pain and sleep assessments:** All are major features of reported Long-COVID and are associated with impact on quality of life [4,5,7,8,11]. Sleep disturbances are associated with chronic inflammation and immune activation.
- **Respiratory assessment:** SARS-CoV-2 is a respiratory virus, and most of the severe morbidity and mortality seen with COVID-19 is due to lung involvement. Respiratory symptoms, parenchymal, and functional abnormalities have been well-described and are common in survivors [9,13].
- **Cardiac assessment:** Significant myocarditis, both acute and chronic, has been described with COVID-19 infection, and concern expressed about long term effects on function [12,17].
- **Renal assessment:** Kidney injury is common with acute SARS-CoV-2 infection, and subclinical inflammation and injury may persist for many months, with progressive decline in kidney function [10].
- **Glucose metabolism assessment:** Diabetes is a strong risk factor for severe COVID-19 disease, as well as for Long-COVID and B-cell dysfunction, often irreversible, in survivors [11,18].
- **Genetic assessment:** SARS-CoV-2, COVID-19, and vaccination immune responses have notable clinical heterogeneity and interindividual differences, whether susceptibility to the virus, severity of COVID-19, or vaccine response, and may be partly ascribed to host genetic factors. Early host

genetic investigations have been limited to acute COVID-19 in European-ancestry individuals, with almost no attention to genetic correlations with Long-COVID [19,20,21].

3. OBJECTIVES AND ENDPOINTS

Primary	
Objectives	Endpoints
To characterise Long-COVID in four cohorts of patients with previous SARS-CoV-2 infection (asymptomatic, symptomatic, severely symptomatic requiring hospitalisation, and those who were vaccinated prior to widespread community exposure).	Incidence, severity, and duration of Long-COVID symptoms.
Secondary	
Objectives	Endpoints
To describe the following characteristics in four cohorts of patients with previous SARS-CoV-2 infection (asymptomatic, symptomatic, severely symptomatic requiring hospitalisation, and those who were vaccinated prior to widespread community exposure): 
• Inflammatory markers• Psychological profiles• Psychosocial exposures• Work performance in employed participants	
• High sensitivity C-reactive protein (hs-CRP)• Interleukin-1β (IL-1β)• Interleukin-6 (IL-6)• Interleukin-8 (IL-8)• Tumour necrosis factor alpha (TNFα)• Tumour necrosis factor alpha receptor-1 (TNFR1)• Monocyte chemoattractant protein-1 (MCP-1)• Headache Impact Test-6 (HIT-6)• Patient Health Questionnaire-9• Generalised Anxiety Disorder 7• PTSD Checklist for DSM-5 - Civilian Version• Mood Disorder Questionnaire• Montreal Cognitive Assessment• Daily Fatigue Impact Scale• COVID-19 related stress questionnaire• Multidimensional Scale of Perceived Social Support• Perceived Stress Scale• Adverse Childhood Experiences tool• Normal activities and work productivity questionnaire

• Sleep quality and disorders• Pain experience• Cardiorespiratory function• Standard laboratory parameters• Renal function• Host genetic factors that may be associated with Long-COVID	
• Pittsburgh Sleep Quality Index• Epworth Sleepiness Scale• Berlin Questionnaire for risk of sleep apnoea• International Restless Legs Syndrome Severity Scale• Sleep quality and mood visual analogue scale• Brief Pain Inventory• Modified Medical Research Council (mMRC) Dyspnoea Scale• Six-minute walk test (distance)• Electrocardiogram (ECG) parameters and morphology• Full blood count• Serum chemistry• Liver function tests• Glucose, glycosylated haemoglobin (HbA1C)• Creatinine clearance• Cystatin-C• Urine dipstick parameters• Urine albumin-to-creatinine ratio• Genotyping results• DNA sequencing results
Exploratory Objectives	

• Various specialised respiratory, cardiac, psychiatric and neuroendocrine, sleep and inflammation, pain, and glucose metabolism parameters will be explored in patients with Long-COVID from four cohorts of participants previously infected with SARS-CoV-2 compared to those with no signs or symptoms of Long-COVID (controls) from the same cohorts.	

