Sample Size	
One hundred (100) participants will be enrolled into each cohort (400 participants overall).
 
Enrolled participants with and without Long-COVID will be assessed for their suitability for various sub-studies. From the eligible participants, up to 30 from each cohort will be randomly selected to participate in each sub-study (while ensuring the requisite ratio of participants with Long-COVID to those without is maintained as applicable for each sub-study). The same participant may participate in more than one sub-study.
 
No formal sample size calculation was performed for this observational study.

Duration	
The duration of participation for each participant will either be a single visit (of approximately 6 hours), or two or more visits depending on whether they are enrolled into any sub-studies.
 
Participants selected for the sleep study will have an overnight admission at the Wits Faculty of Health Sciences sleep laboratory.
 
Enrolment to the study is expected to complete within one year.

Statistical Analysis	
Participants enrolled in the main, and various sub-studies, will be summarised. Demographic data and other baseline characteristics will be summarised overall, per cohort, and per disease status (Long-COVID or no Long-COVID) as relevant.
 
All primary and secondary endpoints will be summarised descriptively overall, per cohort, and per disease status (Long-COVID or no Long-COVID) as relevant, and for various risk factors as deemed appropriate in this exploratory study. Associations between outcomes, COVID-19 history, vaccination status prior to and since infection, and COVID-19 risk factors for severe disease will be explored. Co-factors such as time since initial SARS-CoV-2 infection, and possible confounders such as vaccination, exposure to potential disease-modifying repurposed drugs, and undisclosed vaccination or prior infections, will be accounted for as relevant.
 
Raw genetic genotyping results will be quality controlled by experienced SBIMB bio-informaticists. Association and fine-mapping will be used to investigate links between host genetics and Long-COVID variables generated by the broader study.

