- 2 Written or electronic informed consent to be provide prior to any screening or study-specific assessments, questionnaires or procedures are conducted.
- 3 Including dates of diagnosis through SARS-CoV-2 PCR or antigen testing, or date of positive antibody testing, COVID-19 vaccination dates (if administered), COVID-19 hospitalisation dates (if applicable).
- 4 Including information related to specific risk factors associated with poor COVID-19 outcomes and a detailed history of previous COVID-19 episodes (if applicable).
- 5 Targeting symptoms not covered in other administered surveys and questionnaires.
- 6 Details regarding previous and concomitant medications from the time of the participant's confirmed SARS-CoV-2 infection will be collected.
- 7 Including height and weight, and at least a general, cardiorespiratory, and skin examination and other systems as indicated through reported symptoms.
- 8 Vital signs (blood pressure, pulse rate, respiratory rate, body temperature, and SpO₂) will be measured after 5 min resting.
- 9 A standard 12-lead ECG will be conducted after the participant has rested in the supine position for 10 minutes.
- 10 A blood sample will be collected for full blood count, serum chemistry, liver function, renal function, glucose, HbA1C, and inflammatory markers assessments, and for DNA extraction for genotyping and sequencing.
- 11 Blood (50 mL) and urine (100 mL) samples will be stored for possible future analysis pending emerging information.
- 12 Study team personnel will review each participant's baseline data and identify participants with and without Long-COVID who are eligible for participation in one, or more, sub-study. Invited participants will be randomly selected from the set of eligible participants for each sub-study. Participants who decline the invitation to participate in one, or more, sub-study, will be replaced by a randomly selected, matched-cohort participant where possible.
- 13 Participants will be contact telephonically to inform them of the results of their baseline assessments, and to arrange for follow-up clinical consultations as required for any identified medical or mental health issues. Participants that have been selected for sub-study participation will be invited to return for consent and enrolment into these sub-studies.

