After the baseline visit, participants with Long-COVID will be identified using the WHO clinical definition and general health assessments [2]. Randomly selected sub-groups of participants with, and without, Long-COVID will be selected from each of the four cohorts for additional investigations through participation in the following sub-studies:

- Respiratory evaluation: dyspnoea assessment, high-resolution computed tomography (CT) scan, lung function studies including spirometry and diffusion capacity (DLCO) [Section 7.2.2.1]
- Cardiac evaluation: clinical history and examination, serial blood pressure, six minute walk test (distance), ECG, echocardiogram including speckle tracking, cardiac magnetic resonance imaging (MRI), creatine kinase MB fraction (CK-MB), cardiac troponin T (cTnT), prohormone brain natriuretic peptide (pro-BNP), and possible coronary angiography in patients with acute coronary syndromes and unstable angina [Section 7.2.2.2]
- Psychiatric and neuroendocrine evaluation: questionnaires/surveys, semi-structured interview, home visit, saliva cortisol analysis, collection of diary data, actigraphy, adrenocorticotrophic hormone (ACTH) challenge (cosyntropin sensitivity test [CST]), cellular immunity assessment [Section 7.2.2.3]
- Sleep evaluation: questionnaires, actigraphy with sleep diaries, polysomnography (PSN) [Section 7.2.2.4]
- Pain evaluation: quantitative sensory testing (QST) and conditioned pain modulation (CPM) assessments [Section 7.2.2.5]
- Glucose metabolism evaluation: oral glucose tolerance test (OGTT) including assessment of glucose, insulin, and c-peptide to estimate insulin sensitivity and beta-cell function [16]. [Section 7.2.2.6]

Abnormalities detected in the assessments (including undiagnosed mental health issues) will be managed by on-study medical personnel with referral as appropriate.

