7.2 Sub-Studies

Participants may be invited to take part in more than one sub-study, or none. Up to 30 participants from each cohort will be enrolled into each sub-study. Participants with and without Long-COVID will be age- and gender-matched where possible.

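### Do the exploratory objective and the sub-study selection text define two different control groups?

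*Protocol*

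**What the plan says.** The exploratory objective, in Section 3 and in the synopsis, compares sub-study parameters in participants with Long-COVID "compared to those with no signs or symptoms of Long-COVID (controls) from the same cohorts".

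The text that governs who enters a sub-study is worded differently:

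- Section 4.1: "Randomly selected sub-groups of participants with, and without, Long-COVID will be selected from each of the four cohorts". Cases are identified after the baseline visit by the WHO clinical definition together with general health assessments.
- Synopsis, Sample Size: up to 30 per cohort per sub-study, "while ensuring the requisite ratio of participants with Long-COVID to those without is maintained as applicable for each sub-study".
- Section 1, footnote 12: the study team reviews each participant's "baseline data and identify participants with and without Long-COVID who are eligible for participation in one, or more, sub-study".
- Section 7.2: "Participants with and without Long-COVID will be age- and gender-matched where possible".

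Sections 9.2.1 and 9.2.2 also use two disease-status classes, Long-COVID or no Long-COVID.

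The background bears on what the phrases mean. Section 2.1 says that isolation, fear, hardship and bereavement during the pandemic are factors "all of which contribute to symptoms (psychiatric and sleep disturbances, pain, and other syndromes) reported to be associated with Long-COVID". Section 2.2 states "The diagnosis of Long-COVID is one of exclusion" and cites a review with "over 80% of COVID-19 survivors having at least one symptom, sign, or abnormal" laboratory parameter.

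**The concern.** If the objective means free of every symptom or sign on the Long-COVID list, whatever its cause, then the selection text recruits people whom the objective does not count as controls. Section 2.1 expects such people: psychiatric, sleep and pain symptoms with other causes.

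Two consequences would follow. Some randomly selected non-cases would have no place in the comparison. And the remaining controls would be symptom-free by construction, while the respiratory sub-study repeats the mMRC Dyspnoea Scale (7.2.2.1) and the psychiatric and sleep sub-studies repeat questionnaires (7.2.2.3, 7.2.2.4). Part of those contrasts would come from the definition, and background pandemic symptoms would be read as Long-COVID. Sub-study places are limited, so a wrong choice at invitation is hard to undo later.

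**Working it through.** **1. One participant, both wordings.** Take someone whose sleep has been poor since a bereavement and who is judged at baseline review not to have Long-COVID.

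- Selection text: without Long-COVID, so can be drawn as a comparison participant.
- Objective, read by attribution (no sign or symptom that is *of* Long-COVID): the sleep problem has another cause, so this person is a control. The wordings agree.
- Objective, read as a symptom list (nothing on the list, whatever the cause): not a control. The wordings disagree.

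The attribution reading fits the text better. The phrase ties the signs and symptoms to Long-COVID, and Section 2.2 makes that a diagnosis of exclusion. No passage creates a third group, and the Section 9.2 summaries have only two classes. Because footnote 12 works from baseline data, later CT, DLCO or polysomnography results do not reclassify anyone.

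**2. Size if the list reading were applied.** The protocol gives no figure to reproduce. Inputs: 100 per cohort and up to 30 per sub-study (protocol); 1:1 ratio, so 15 non-cases drawn per cohort (assumed); Long-COVID share p of 30–50% (assumed); share free of all symptoms f of 20–50%, where 20% is the complement of the review's figure of over 80% and the rest is assumed.

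Per cohort, W = 100(1 − p) are without Long-COVID and F = min(W, 100f) are symptom-free. The expected number of list-reading non-controls among 15 is 15(W − F)/W.

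| f | p = 30% (W = 70) | p = 40% (W = 60) | p = 50% (W = 50) |
|---|---|---|---|
| 20% | 15 × 50/70 = 10.7 | 15 × 40/60 = 10.0 | 15 × 30/50 = 9.0 |
| 30% | 15 × 40/70 = 8.6 | 15 × 30/60 = 7.5 | 15 × 20/50 = 6.0 |
| 40% | 15 × 30/70 = 6.4 | 15 × 20/60 = 5.0 | 15 × 10/50 = 3.0 |
| 50% | 15 × 20/70 = 4.3 | 15 × 10/60 = 2.5 | 0 |

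The range is 0 to 10.7 of 15. Under the attribution reading every cell is 0.

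**3. A single symptom.** Section 2.2 gives dyspnoea as 24%. If it were 24% in cases and non-cases alike, 60 non-cases (4 × 15) would include 0.24 × 60 = 14.4 with dyspnoea. List-reading controls would include none, a 24-point difference where the true one is 0. At 10% it would be 6 of 60 against 0, or 10 points.

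**4. How much circularity belongs to the wording.** Suppose the Long-COVID label falls at random among symptomatic people, so that it adds nothing once symptoms are known. Cases then have the mean of all symptomatic people, and non-cases are a mixture of F symptom-free and W − F symptomatic people. The contrast against all non-cases is therefore F/W times the contrast against symptom-free controls. A simulation of two million people, with a measure correlated 0.3 with symptom burden (assumed), gave 0.52 SD against symptom-free controls at 80% symptomatic and 0.48 SD at 50%. Hence, against all non-cases:

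- 80% symptomatic, 20% or 40% Long-COVID: 0.52 × 20/80 = 0.13 SD; 0.52 × 20/60 = 0.17 SD.
- 50% symptomatic, 20% or 40% Long-COVID: 0.48 × 50/80 = 0.30 SD; 0.48 × 50/60 = 0.40 SD.

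Some difference on symptom measures is present under either wording, because cases are chosen on symptoms. Symptom-free controls enlarge it, by much or by little depending on how common symptoms are.

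**The case for a change.** The best case for a change is that the protocol nowhere equates the two phrases, that its own background expects symptoms from other causes, and that selection happens once. An analysis plan can choose whom to compare, but it cannot recover symptomatic non-cases who were never invited. One agreed phrase would cost nothing.

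What stands is that the wordings differ and that a strict reader could take the objective the second way. The rest is weaker. The staff who invite participants work from footnote 12 and Sections 4.1 and 7.2, which all say with and without Long-COVID, so symptomatic non-cases are eligible to be drawn. Baseline symptoms are recorded for everyone, so a symptom-free subset can still be examined at analysis.

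The figures cannot carry the argument either. The review's figure of over 80% includes laboratory abnormalities and comes from other populations. Here it would be applied to four unlike cohorts, one of them asymptomatic at infection, all at least six months on, although Section 2.2 says symptoms tend to resolve. The 24% for dyspnoea is a share of all survivors in that review, not of people without Long-COVID. Section 5.4.2 also removes smokers, people exposed to biomass fuel, and those with earlier treated respiratory illness or tuberculosis from the respiratory sub-study, and with them major other causes of dyspnoea.

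**Conclusion.** No change is needed. The difference is one of loose phrasing in an exploratory objective. Read with the diagnosis-of-exclusion statement and the two-class selection and analysis text, both phrases mean participants not classified as having Long-COVID at baseline review, and the built-in effect of the wording is zero. Analysts who follow the selection rule as written will obtain a sound exploratory contrast.

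Only the strict reading gives a non-zero effect. Its size, 0 to 10.7 of 15 per cohort, depends on an assumed Long-COVID share, ratio and symptom-free share, and the protocol cannot narrow it. Whether to prefer symptom-free controls or all non-cases is a fair trade-off: the former sharpen contrasts but build in part of them, while the latter keep background symptoms in the comparison at the price of smaller differences. The main-study cohort summaries are unaffected. The analysis plan and sub-study plans are not at hand and may already define controls. Using one phrase throughout would be harmless tidying if the protocol were amended for another reason.
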